### 2.6. STUDY PROCEDURE

Once the desired sample size has been reached, a randomized controlled trial with 6 measurement time points will be conducted in which participants will be randomly assigned to either the intervention group or the waiting control group.

The intervention group receives access to the online training after randomization. The waiting control group receives access only after the first follow-up measurement (3 months after the post-measurement). Two further follow-up measurements follow (6 and 12 months after the post-measurement). The detailed time schedule can be seen in the attached flow chart. The entire data collection and intervention will be online. Neither the participants nor the study team will be blinded.

Within the practice modules, the following interventions and measurements are planned (in weeks 3 and 5, a self-care intervention is planned, in weeks 4 and 6, a self-compassion intervention is planned):

Practice phase: trainings and measurements (weeks 3 to 6; with buffer to complete the modules for weeks 7 & 8)				
Week 3	Day 1	st 1.1 pre state assessment pre-intervention	Weekly intervention (approx. 30 min)	st 1.1 post state assessment post-intervention
	Day 2	st 1.2 pre state assessment pre-intervention	Daily training intervention, 1st session (approx. 5-10 min)	st 1.2 post state assessment post-intervention
	Day 3	st 1.3 pre	Daily training intervention, 2nd session (approx. 5-10 min)	st 1.3 post
	Day 4	st 1.4 pre	Daily training intervention, 3rd session (approx. 5-10 min)	st 1.4 post
	Day 5	st 1.5 pre	Daily training intervention, 4th session (approx. 5-10 min)	st 1.5 post
	Day 6	st 1.6 pre	Daily training intervention, 5th session (approx. 5-10 min)	st 1.6 post
	Day 7	st 1.7 pre	Daily training intervention, 6th and last session (approx. 5-10 min)	st 1.7 post
Week 4	Day 1	st 2.1 pre state assessment pre-intervention	Weekly intervention (approx. 30 min)	st 2.1 post state assessment post-intervention
	Day 2-7	st 2.2 pre- st 2.7 pre	Daily training intervention, 2nd – 6th session (approx. 5-10 min)	st 2.2 post- st 2.7 post
Week 5 - 6	...	...	...	...

Legend: stx.x pre = state assessment pre-intervention; stx.x post = state assessment post-intervention

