### 2.2. TREATMENT GROUPS

Treatment: Participants in the intervention group will gain access to the 6-week online resilience intervention "resiLIR Healthcare Professionals".

The waitlist control group will receive access to the intervention after the first follow-up assessment (3 months post-intervention).

Randomisation process: Stratified randomization is used, with age and gender as influencing factors. Randomization is performed using randomized numbers generated with Microsoft Excel. Due to the nature of the intervention, no blinding and subject replacements are planned.

Subject replacement: not applicable.

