**Exclusion criteria:**

- In PP analysis, Participants will be excluded from respective analyses if
  - they fill in less than 50% of questionnaires at a specific measurement point (e.g., pre-test) which address the primary outcome and secondary outcomes trained in the intervention
  - they fill in less than 50% of a specific questionnaire.
  - they have an implausibly short time for completing the assessments (DEG\_TIME in SoSci-Survey).
  - there is an abnormality in data (e.g., rating always the highest/ lowest on several scales).
- Participants will be excluded from the whole analysis if
  - they do not agree with the terms of usage, usage of data and privacy policy.
  - they state that their data cannot be used in a sensible way.

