#### CLASSIFICATION OF PROTOCOL VIOLATION

Exclusion of participants due to protocol violations will be reported in the methods / results section. To examine outliers in the questionnaire data, boxplots will be created.

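### The study team is left unblinded with no masked data review, so the judgement-based per-protocol exclusions can be made with the arm known

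*SAP*

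**What the plan says.** On blinding, SAP 2.2 (Treatment groups) states "Due to the nature of the intervention, no blinding and subject replacements are planned", and 2.6 (Study procedure) repeats it for everyone involved: "Neither the participants nor the study team will be blinded". The same section says "The entire data collection and intervention will be online".

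On record-level decisions, section 3 (Populations of analysis) introduces a list with "In PP analysis, Participants will be excluded from respective analyses if". Two items on that list are numeric, each at 50% of questionnaires or items. The other two are not:
- "they have an implausibly short time for completing the assessments". DEG_TIME is named as the indicator here and under Survey in 4.3, but neither place gives a cut-off.
- "there is an abnormality in data (e.g., rating always the highest/ lowest on several scales", which is an example and not a rule.

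Section 3 also lists two exclusions from the whole analysis. One is refusal of the terms and privacy policy. The other is "they state that their data cannot be used in a sensible way". The participant triggers both. The intention-to-treat set is made up of valid data sets, and valid is not defined.

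Section 5.1, under Classification of protocol violation, says exclusions will be reported and adds "To examine outliers in the questionnaire data, boxplots will be created". No threshold and no consequence follow. Nowhere does the SAP provide for a masked analyst, a coded arm label or a data review before the arms are known.

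**The concern.** A person who receives or waits for a training programme cannot be blinded. The outcomes of H1–H11 are questionnaires completed by those same people, so this source of bias stays. Bias from data handling can be avoided. Nothing about a training programme requires the person who flags fast or odd response patterns to see the arm, and an online questionnaire file can be exported without that column.

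Unblinded handling would matter little if the rules were mechanical. Here two exclusions are open to judgement and no masked step protects them. Doubtful records could be dropped when they are unfavourable to training in the intervention arm, or favourable in the waitlist arm, without anyone intending it. The per-protocol comparison is one of two planned analyses, and the SAP names neither as the primary one.

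**Working it through.** **Which decisions are exposed**

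| Decision (SAP place) | Rule fixed? | Analysis affected |
|---|---|---|
| Under 50% of questionnaires or items (3) | Yes | Per-protocol |
| Too-fast completion (3) | Indicator named, no cut-off | Per-protocol |
| Abnormal data (3) | Example only | Per-protocol |
| Refused terms; own data declared unusable (3) | Participant decides | All |
| Valid data set (3) | Undefined | Intention-to-treat |
| Outliers (5.1) | Boxplot only, no stated action | Any, if action follows |
| Intervention completion (5.1) | Theory modules plus at least 50% of exercises | Per-protocol |

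The completion rule is stated numerically but reveals the arm, because it rests on platform usage.

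**Illustration of size.** The SAP has no figure on this point to reproduce. Its own inputs are 120 per arm and 40% dropout, so 120 × (1 − 0.40) = 72 per arm. The rest is assumed: no true effect, standard normal outcomes, an independent t-test at two-sided 0.05, and a share q of records questionable at random in both arms. A questionable record is dropped only if it lies on the unfavourable side of the mean (below it in the intervention arm, above it in the waitlist arm, with higher scores better).

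- Share dropped per arm: q/2. The mean of a half-normal is √(2/π) = 0.798.
- Shift over both arms: 2 × (q/2) × 0.798 / (1 − q/2).
- Records left per arm: m = 72(1 − q/2). Standard error: √(2/m).
- False positives favouring training: about P(Z > 1.96 − shift/SE).

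| q | Dropped per arm | Shift by formula | SE | 1.96 − shift/SE | False positives by formula | Simulated shift; rate |
|---|---|---|---|---|---|---|
| 5% | 1.8 | 0.0399/0.975 = 0.041 | 0.169 | 1.72 | 4.3% | 0.042; 4.2% |
| 10% | 3.6 | 0.0798/0.95 = 0.084 | 0.171 | 1.47 | 7.1% | 0.083; 7.0% |
| 15% | 5.4 | 0.1197/0.925 = 0.129 | 0.173 | 1.21 | 11.3% | 0.128; 11.5% |

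The simulation used 10,000 runs per row. The nominal rate in this direction is 2.5%. If only half of the questionable records are handled selectively, a 20,000-run simulation gives shifts of 0.018, 0.041 and 0.061 SD and rates of 3.0%, 4.4% and 5.5%.

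**Is the table a ceiling?** No. It assumes that being questionable is unrelated to the score, yet the SAP's own example of abnormal data is extreme responding. Dropping the k least favourable values from the intervention arm alone (20,000 runs, 72 per arm, no true effect) gives:

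| k | Shift (SD) | False positives favouring training |
|---|---|---|
| 1 | 0.035 | 4.3% |
| 2 | 0.062 | 6.2% |
| 3 | 0.089 | 8.4% |
| 5 | 0.14 | 14.5% |

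Five extreme records from one arm therefore do more than about 5.4 random ones from each arm.

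**The case against.** The case on the other side is substantial, and much of it stands.

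- **Who decides is not stated.** A reader might infer that the SAP says exclusions will be made with the arm known. It says the team is unblinded, but not who cleans the data or when. The arm being known to those who decide is an inference from the blanket statement and the absence of any masked role. Likewise, 2.2 attaches its reason to blinding as a whole. That the reason does not reach data cleaning is a judgement on its merits, not something the SAP concedes.
- **Scope.** A reader might infer that the intention-to-treat result is equally at risk. It is not: the two judged exclusions are confined to the per-protocol analysis, and the whole-analysis exclusions come from the participant.
- **Outliers.** A reader might infer that outliers will be removed. The SAP commits only to looking at boxplots.
- **Visibility.** Exclusions for protocol violations will be reported and publication will follow CONSORT, so a lopsided pattern would probably show. That helps detection afterwards but does not prevent the bias.
- **Cut-offs first.** Fixed thresholds would remove most of the discretion even without masking. This is right, and they belong in the fix. An open category such as abnormal data is still likely to leave some judgement, so masking keeps its value.

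**Conclusion.** The point holds as a cheap improvement, mainly for the per-protocol comparison. The reason given for an unblinded team does not prevent masked data cleaning, two per-protocol exclusions rest on judgement, and no masked review is planned. The intention-to-treat analysis is exposed at record level only through the undefined term valid and whatever might follow the boxplots.

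The bias is possible, not demonstrated, and its size cannot be derived from the SAP. The range in the working depends on assumed shares of questionable records and on fully selective handling. It uses a plain t-test where the SAP plans a mixed ANCOVA with the baseline as covariate, and it takes 72 per arm although the completion rule will reduce the per-protocol set further. A reader might take the range as a worst case, but the extreme-record calculation shows that it is not.

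Masking removes the dependence of these decisions on the arm label. It does not make the per-protocol comparison unbiased, because the completion rule still selects participants after randomisation.

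**What to change.** 1. In 2.2 and 2.6, limit the unblinded statement to participants and platform support.
2. Before data access, set the DEG_TIME cut-off and the abnormal-pattern rule, define a valid data set, and say what, if anything, follows from a boxplot outlier.
3. Make and lock the validity, speed, abnormal-pattern and any outlier decisions on a t0–t3 questionnaire file without the arm label. Withhold variables that reveal the arm: usage statistics, state queries, the feedback questionnaire, satisfaction (CSQ-I), relationship to the intervention (mARM) and negative effects (INEP).
4. After the lock, merge the arm code and usage data and apply the completion rule of 5.1 mechanically.

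The cost is SAP wording plus one extra export and merge step. The drawback is that usage-based rules must wait for the merge.

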### 3. POPULATIONS OF ANALYSIS

We will conduct both an intention to treat (ITT) analysis as well as a per protocol (PP) analysis (see also “5.1. Statistical methodology”), with the following criteria:

**Inclusion criteria** (included in ITT analysis):

- All valid data sets

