#### HANDLING OF MISSING DATA

- On the one hand, the data will be analysed according to the "intention-to-treat" principle, with missing values being replaced using appropriate imputation methods.
- On the other hand, the results will be reported as "per-protocol" analysis, in which only those cases are considered that have gone through the study procedure as defined by protocol. We consider the intervention to be completed for participants who, in addition to the theory modules, completed at least 50% of the weekly interventions and the daily training interventions. To note, a maximum of 4 weekly interventions with 6 daily interventions can be reached. In the per-protocol analysis, only these participants will be included. To control for influences of compliance, usage of intervention will be examined as covariate in an exploratory analysis.

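### The ITT set is not defined as all randomised participants: 'valid' is left undefined, and a self-declaration rule with no stated time point removes people from ITT

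*SAP*

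**What the plan says.** Section 3 of the SAP announces an ITT and a PP analysis. Under the heading for data "included in ITT analysis" there is one line: "All valid data sets". The section does not define validity, and neither it nor the rest of the SAP states that everyone randomised is analysed in the assigned group.

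The exclusion list then has two tiers:

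- **PP only.** The first tier opens with "In PP analysis, Participants will be excluded from respective analyses if". It covers low completion of a measurement point or a questionnaire, implausibly fast completion, and abnormal response patterns.
- **All analyses.** The second tier opens with "Participants will be excluded from the whole analysis if" and has two grounds: "they do not agree with the terms of usage, usage of data and privacy policy", and "they state that their data cannot be used in a sensible way".

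Section 5.1, under the handling of missing data, invokes the intention-to-treat principle with "missing values being replaced using appropriate imputation methods". Sections 2.2 and 2.6 state that there is no blinding, and section 2.6 gives six measurement time points. Hypothesis 1 in section 4.4 compares the groups on the primary outcome at t2 and t3 against t0.

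**The concern.** An ITT set protects the randomised comparison because membership is fixed at allocation. Here membership depends on two things that are not fixed then: an undefined judgement of validity, which an unblinded study team would have to make, and a participant's own statement about the quality of their data.

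The second is an explicit rule, not a missing detail. Nothing ties it to t0 or to the period before allocation. Taken as written, a declaration at t2 or t3 removes the whole participant, usable baseline data included. If such declarations are commoner in one arm, or come from people with different outcomes, the primary comparison is no longer between the groups as randomised. The report would nevertheless call the analysis ITT, and a reader would take it as all randomised.

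**Working it through.** **Reading the rules together.** The SAP gives no figure for the size of the ITT set. The one anchor is section 2.1: 240 participants, 120 per group.

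| Situation | PP (section 3) | ITT (section 3) | Imputed under section 5.1? |
|---|---|---|---|
| Less than 50% completed, too fast, or abnormal pattern | Excluded from the respective analysis | No stated exclusion | Missing values yes |
| Dropout with missing values | Depends on completion of the intervention | No stated exclusion | Yes |
| No agreement to terms, data use or privacy policy | Excluded | Excluded | No |
| Own statement that the data are not usable | Excluded | Excluded | No |
| Data set not 'valid' for another reason | Not stated | Cannot be determined | Cannot be determined |

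The objective quality flags therefore leave a participant in ITT, while the most subjective flag takes the participant out. An all-randomised set has 240 members. The set described in section 3 has 240 minus a number that is not fixed in advance.

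**Illustrative size.** The inputs f and δ are assumptions; neither is in the SAP. Let an excess fraction f of one arm be removed, with a mean δ SD worse than the mean of the whole arm, and nobody be removed from the other arm. The mean of those who remain, and so the contrast, shifts by

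shift = f × δ / (1 − f)

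- f = 5% (6 of 120), δ = 0.5: 0.05 × 0.5 / 0.95 = 0.026 SD
- f = 10% (12 of 120), δ = 0.5: 0.10 × 0.5 / 0.90 = 0.056 SD

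Against the planned effect of 0.50 (section 2.5) these are 0.026 / 0.50 = 5% and 0.056 / 0.50 = 11%.

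If the same fraction with the same deviation is removed from both arms, the two shifts cancel and the contrast is unchanged.

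**Effect on the test.** The same shift can be written q × D, where q is the fraction removed and D is measured against those who remain, D = δ / (1 − f). For a two-sided 5% t-test with about 120 per group and no true effect:

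- q = 2%, D = 0.5: bias 0.010 SD, type I error about 0.051
- q = 5%, D = 0.5: bias 0.025 SD, type I error about 0.054
- q = 10%, D = 0.5: bias 0.050 SD, type I error about 0.067

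These are approximations for an unadjusted two-group comparison and take no account of dropout.

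**The case against.** The strongest reply is that section 3 already does most of what ITT requires. The completion, speed and pattern rules are confined to PP, so poor or incomplete data stay in ITT, and section 5.1 imputes what is missing. On this reading 'valid' most naturally means not caught by the two exclusions that apply to every analysis. One of those, non-agreement with the terms, resembles a consent step and is unobjectionable. What remains is one narrow rule that may rarely be used.

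Much of this stands. It limits the point to one rule and one word, but it does not remove it: the natural reading of 'valid' is not written down, and the self-declaration rule still reaches ITT.

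A reader might also infer three stronger things that the SAP does not support:

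- **That the statement is made after randomisation, with knowledge of the arm.** The SAP names no survey and no time point for it. The text permits this timing but does not state it. If the question is asked only before allocation, this source of bias disappears.
- **That removal would favour the intervention, perhaps by a large amount.** Nothing in the SAP shows that people who disown their data have worse stressor-reactivity scores or cluster in the intervention group. Disengaged participants may simply stop answering; they would then be among the 40% dropout assumed in section 2.5 and be imputed. A 20% excess in one arm (24 of 120) would give 0.20 × 0.5 / 0.80 = 0.125 SD, a quarter of the planned effect, but nothing suggests a figure that high.
- **That sections 3 and 5.1 cannot both hold.** They can, as an ITT analysis with stated exclusions. The fault is that such a set is a modified ITT and is not labelled so.

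The SAP also promises, under the classification of protocol violation, to report exclusions. It does not ask for counts by arm, and reporting does not put anyone back into the set.

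**Conclusion.** The point holds in a limited form. The analysis labelled ITT is not defined as all randomised, and one stated rule allows randomised participants to leave it on their own declaration, at a time the SAP does not fix, in an unblinded trial with repeated surveys after allocation. Arm-dependent removal is possible under the text; it is not shown to occur.

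The SAP gives no basis for the direction or size of a bias. The range of about 0.03 to 0.06 SD rests on three assumptions: 5% to 10% excess removal, all of it in one arm, and a mean 0.5 SD worse among those removed. The defect lies in the wording and does not depend on these figures. It should be corrected because it touches the primary comparison and the remedy is cheap.

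**What to change.** In section 3:

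1. Define the ITT set as all randomised participants, analysed in the group to which they were assigned, and delete the reference to valid data sets.
2. Keep only lack or withdrawal of consent to data use as a ground for removal from ITT.
3. Treat a survey that its respondent declares unusable as missing at that time point, keep the participant's other surveys, and handle the gap by the missing-data method of section 5.1.
4. Apply the self-declaration exclusion only in PP or in a sensitivity analysis.
5. State at which time points the question is asked, and report the declarations by arm and time point.

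The cost is a few sentences in the SAP and a few more imputed values. No change to the sample size or data collection follows from it.

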**Exclusion criteria:**

- In PP analysis, Participants will be excluded from respective analyses if
  - they fill in less than 50% of questionnaires at a specific measurement point (e.g., pre-test) which address the primary outcome and secondary outcomes trained in the intervention
  - they fill in less than 50% of a specific questionnaire.
  - they have an implausibly short time for completing the assessments (DEG\_TIME in SoSci-Survey).
  - there is an abnormality in data (e.g., rating always the highest/ lowest on several scales).
- Participants will be excluded from the whole analysis if
  - they do not agree with the terms of usage, usage of data and privacy policy.
  - they state that their data cannot be used in a sensible way.

### 4. OUTCOME VARIABLES

#### 4.1. PRIMARY OUTCOME

- Resilience measured with *Stressor-Reactivity-Score* (SR-Score)

#### 4.2. SECONDARY PARAMETERS OUTCOMES

##### Outcomes related to the intervention and the primary outcome

- Resilience measured with *Brief Resilience Scale* (BRS; Chmitorz et al., 2018)
- Mental Health measured with *General Health Questionnaire* (GHQ-12; Schnitz et al., 1999)
- Self-Compassion measured with *Self-Compassion Scale Deutsch* (SCS-D; Hupfeld & Ruffieux, 2011)
- Mindfulness measured with *Mindful Attention and Awareness Scale* (MAAS-Short; Höfling et al., 2011)
- Perceived Stress measured with *Perceived Stress Scale* (PSS-2+2; Schäfer et al., in preparation)
- Stressors measured with *Mainz Inventory of Microstressors* (MIMIS; Chmitorz et al., 2020)
- Life Events measured with *Life Events Checklist-5* (LEC-5; Krüger-Gottschalk et al., 2017)
- Anxiety/ Depression measured with *Generalized Anxiety Disorder-7* (GAD-7) and *Patient Health Questionnaire-9* (PHQ-9; Löwe et al., 2002)
- Self-Care measured with *Hamburger Selbstfürsorgefragebogen* (Hamburg Self-Care Survey; Harfst et al., 2009)
- Burnout measured with the German version of the *Maslach Burnout-Inventory* (MBI-D; Büssing & Perrar, 1992)
- Work-Life-Balance measured with the *Trierer Kurzsкала zur Messung von Work-Life Balance* (TKS-WLB; Syrek et al., 2017)

##### Further (exploratory) outcomes

- Optimism measured with *Optimism-Pessimism-Scale* (SOP-2; Kemper et al., 2014)
- Positive reappraisal measured with subscale of *Cognitive Emotion Regulation Questionnaire* (CERQ; Loch et al., 2011)
- Acceptance measured with subscale of *Cognitive Emotion Regulation Questionnaire* (CERQ; Loch et al., 2011)
- Positive (Re-)appraisal measured with *Positive Appraisal Style Scale Content* (PASS-content) and *Positive Appraisal Style Scale Process* (PASS-process; Petri-Romao et al., 2021)
- Social Support measured with *Osloer Social Support Scale* (OSS-3; Kocalevent et al., 2018)
- Control beliefs with *Internal-External Locus of Control Short Scale-4* (IE-4; Kovaleva et al., 2014)
- Meaning measured with subscale of *Comprehensive Inventory of Thriving* (CIT; Hausler et al., 2017)

- Self-Efficacy measured with *German Version of Self-Efficacy Short Scale* (Allgemeine Selbstwirksamkeit Kurzsкала, ASKU; Beierlein et al., 2014)
- Coping measured with *Coping Orientation to Problems Experienced Inventory* (Brief-COPE; Knoll et al., 2005)
- Self-Esteem measured with *German Single-Item Self-Esteem Scale* (G-SISE; Brailovskaia & Margraf, 2020)
- Positive Affect measured with subscale of *Positive and Negative Affect Schedule* (PANAS; Breyer & Bluemke, 2016)
- Life Satisfaction measured with *Satisfaction with Life Scale* (SWLS; Janke & Glöckner-Rist, 2012)
- Well-Being measured with *WHO-5 Well-Being Index* (Brähler et al., 2007)
- Functionality measured with *World Health Organization Disability Assessment Schedule* (WHODAS 2.0; Üstün et al., 2010)
- Coping Flexibility measured with *Coping Flexibility Questionnaire Revised* (CFQ-R; Kato, 2012)
- Satisfaction with Intervention measured with *Client Satisfaction Questionnaire-Intervention* (CSQ-I; Boß et al., 2016)
- Adverse Effects measured with *Inventory for the Assessment of Negative Effects of Psychotherapy* (INEP; Ladwig et al., 2014)
- Relationship to Intervention measured with *Mobile Agnew Relationship Measure* (mARM; von Wulffen et al., 2022)
- Sense of Coherence measured with *Sense of Coherence Scale* (SOC-29; Singer et al., 2007)
- Mental Health Literacy measured with *Mental Health Literacy Questionnaire* (MHLQ, Dias et al., 2018), *Mental Health Literacy Scale* (MHLS; O'Connor & Casey, 2015), *Mental Health Knowledge Schedule* (MAKS; Evans-Lacko et al., 2010), *Health Literacy Survey EU 16* (HLS EU 16; Jordan & Hoebel, 2015), *eHealth Literacy Scale* (eHEALS; Soellner et al., 2014), *Well-being Literacy Scale* (Hou et al., 2021), *STRESS K-10* (Giesinger et al., 2008), *Fragebogen zur Erhebung des Wissens über psychosoziale Versorgungsstrukturen* (Questionnaire to survey knowledge of psychosocial care structures; Fritz, 2021)
- Belief Towards Mental Illness Scale (Hirai & Clum, 2018)
- Help-seeking behaviour measured with *General Help Seeking Scale* (GHSS; Rickwood et al., 2005) and *Attitudes Toward Seeking Professional Psychological Help* (ATSPPH; Kessler et al., 2015)
- Work engagement measured with the *Utrecht Work Engagement Scale* (UWES-9; Schaufeli et al., 2006)
- Perceived work stress measured with a German translation of the *Perceived Occupational Stress Scale* (Marcatto et al., 2022)

